8.5 Study Termination

NCI, DCP as the study sponsor has the right to discontinue the study at any time. The FDA also has the authority to discontinue the study at any time.

9. CORRELATIVE/SPECIAL STUDIES

9.1 Rationale for Methodology Selection

The MUC1 ELISA is an established assay that has been used to monitor many clinical trials as well as IgG response in large cohorts of patients on other studies. It has been validated as highly reproducible. The set-up includes positive and negative control anti-MUC1 antibodies that allow comparison of results between different studies. Nevertheless, in this trial, each patient will also be his/her own control as we will compare post-vaccination titers with pre-vaccination baseline. All time points will be assayed simultaneously and multiple times. See Section 10.2.2 for details.

9.2 Comparable Methods

This study will employ procedures that have been validated previously for clinical use.

10. SPECIMEN MANAGEMENT

10.1 Laboratories

Heparinized whole blood collected at all locations will be shipped to the University Of Pittsburgh School Of Medicine. [name] will receive and record the specimens, and he will also be responsible for processing the blood into plasma and PBMC. PBMC will be frozen at -70 to -80°C in human serum with 20% DMSO and plasma will be frozen at -20°C. [name] will run ELISA assays for anti-MUC1 IgG and FACS analysis of % MDSC. Approximately 50% of plasma and 25% of the live cells will be shipped to the Biorepository at the Mayo Clinic for storage and later release when requested for additional biomarker studies.

Unstained slides from tissue blocks of the qualifying advanced adenoma and for adenomas detected at the time of surveillance colonoscopy that determines adenoma recurrence (baseline and recurrent adenomas) will be collected at each site and shipped to the Mayo Clinic. They will then be batched and shipped to the University of Pittsburgh for subsequent immunostaining and other assays.

10.2 Collection, Handling, and Shipping Procedures

10.2.1 Specimen Kits and Shipping Instructions

Research blood kits will be provided by BAP Kit Building (Biospecimen Accessioning and Processing Core Facility). Collection, handling, and shipping instructions will be included with each kit. Participating Sites may obtain research blood kits by faxing the Supply Order Form to the number provided (found in the Forms Packet). At least two weeks should be allowed to receive the shipping kits. Kits will be sent via FedEx® Ground at no additional cost to the participating institutions. They will not be forwarded by FedEx® rush delivery service unless the participating institution provides their own FedEx® account number. CPN will not cover the cost for rush delivery of kits.

Because charges are incurred for all outgoing kits, a small, but sufficient, supply of specimen collection kits should be ordered prior to participant entry.

- ALL sections of the requisition form and specimen collection labels must be completed and legible.
- Blood specimens should be sent over night via FedEx® on cold packs **Monday - Thursday ONLY**.
- All samples must be shipped to the address provided on the specimen shippers (See Section 10.2.2).

All samples will be shipped in compliance with the International Air Transport Association (IATA) Dangerous Goods Regulations.

10.2.2 Research Blood Specimens

Research blood specimens will be collected according to the table in Section 7.1. Blood specimens must be collected **M-Th only** and shipped overnight for next day analysis. Detailed instructions for collecting, processing, labeling, and shipping the specimens can be found in the instructions provided in each blood specimen kit.

Blood specimens will be sent to:

[name], [name]
[name]
[contact] or [contact]; [contact]; Email: [contact]

For tracking purposes, participating organizations will telephone or email the following two individuals to inform them that specimens are being sent to the University of Pittsburgh.

1. **[name],**
Email: [contact]
[contact]
2. **[name], Biospecimens Resource Manager**
Email: [contact]
[contact]

Upon receipt of the overnight shipment or immediately after collection, heparinized blood will be centrifuged over a density gradient (Ficoll) to separate the plasma and PBMC. Plasma will be collected, aliquoted, and stored at -20°C. PBMC will be washed several times, aliquoted, slowly frozen to -70 to -80°C in human serum with 20% DMSO and stored in the vapor phase of liquid nitrogen.

Measurement of the vaccine-induced anti-MUC1 IgG will be determined by the Enzyme-Linked Immunosorbent Assay (ELISA) that was established in [name] laboratory and successfully used to measure anti-MUC1 responses in humans and mice. The procedure is as follows: Immulon 4 (Thermo-Fisher Scientific, MA) microtiter plates are coated overnight at 4°C with 1µg of synthetic MUC1 100mer peptide (vaccine antigen) dissolved in 0.9% Dulbecco phosphate buffered saline (PBS). Corresponding control plates receive PBS but no antigen. The plates are washed three times with and incubated with 2.5% bovine serum albumin (BSA) in PBS (PBS-BSA) to fully coat the microtiter plate wells with protein and block non-specific binding. PBS-BSA is removed and plasma diluted in PBS-BSA added to the wells. After one-hour incubation at room temperature the plates are washed five times with PBS with 0.1% tween-20 (Sigma-Aldrich, MO), and alkaline phosphatase-conjugated anti-human IgG secondary antibody (Sigma-Aldrich) in PBS-BSA added. Following a one-hour incubation the plates are washed five times and the substrate, p-nitrophenyl phosphate (Sigma-Aldrich), added to each well. The reaction is

terminated after one hour by adding 0.5M NaOH. The results are read at optical density (OD) 405nm on a spectrophotometer. The OD values from the control wells containing no antigen are subtracted from the OD values in test wells coated with peptide. Every sample is assayed multiple times at multiple dilutions, in at least triplicate wells. The results can be expressed wither as OD values or control antibody of a known titer, included in the assay, is used to convert the OD values to titers.

For detecting Myeloid-Derived Suppressor Cells (MDSC), PBMC will be thawed and stained with APC-labeled mouse anti-human CD11b antibody (clone: ICRF44, BD Biosciences), PE-Cyanine 7 (PE-Cy7) labeled mouse anti human CD14 antibody (clone: M5E2, BD Biosciences), PE-labeled mouse anti human CD33 antibody (clone: WM53, BD Biosciences) and FITC-labeled mouse anti human HLA-DR antibody (clone: G46-6, BD Biosciences). MDSC will be defined by flow cytometry as CD11b⁺ CD33^{+ /low} HLA-DR^{- /low} cells.

10.2.3 Tissue Specimens

Paraffin blocks and/or unstained slides from the polyps/adenomas removed during routine colonoscopy, pre- and post-intervention, will be requested from the institution at which the procedure was performed.

Tissue paraffin sections will be deparaffinized by baking overnight at 59°C. Endogenous peroxidase activity will be eliminated by treatment with 30% H₂O₂ for 15 min at room temperature. Antigen retrieval will be performed by microwave heating in 0.1% citrate buffer. Nonspecific binding sites will be blocked with Protein Blocking Agent (Thermo-Shandon Corp). Sections will be immunostained with anti-MUC1 antibody HMPV, which recognizes all forms of MUC1 by binding the epitope APDTR in the VNTR region in a glycosylation-independent manner (BD Pharmingen) and anti-MUC1 antibody VU-4H5 (Santa Cruz Biotechnology), which recognizes the epitope APDTRPAP in the VNTR region of hypoglycosylated MUC1 (Santa Cruz Biotechnology). Staining will be performed by the avidin-biotin peroxidase complex (ABC) method with a commercial kit (Vectastain ABC kit, Vector Laboratories). Color development will be performed by 3,3'-Diaminobenzidine (DAB) kit (BD Pharmingen).

Institutions that are unable to submit paraffin blocks may send five 5-micron unstained slides from each advanced adenoma as an alternative. Paraffin blocks and/or slides must be labeled with the participant ID number, specimen type, specimen number, and date of collection. Every effort must be made to make certain the specimen number on the block and/or slide labels corresponds to the polyp or adenoma number reported on the Colonoscopy Report CRF.

Send blocks/slides to:

CPN PC Office (Study MAY2013-01-01)
[name]
[name]

10.3 Tissue Banking

Biologic specimens collected during the conduct of each clinical trial that are not used during the course of the study will be considered deliverables under the contract and thus the property of the NCI.

At study completion, remaining frozen biologic specimens will be labeled (study number, participant ID number, specimen type, specimen number, date of collection) batched, and shipped (overnight, M-Th only) for banking/long term storage to:

Biospecimens Accessioning and Processing (BAP) Freezer
[name]

At study completion, remaining paraffin blocks and slides will be labeled (study number, participant ID number, specimen type, specimen number, date of collection) batched, and shipped for banking/long term storage to:

CPN PC Office (Study MAY2013-01-01)
[name]
[name]

NCI reserves the option to either retain or relinquish ownership of the unused biologic specimens. If NCI retains ownership of specimens, the Contractor shall collect, verify and transfer the requested biologic specimens from the site to a NCI-specified repository or laboratory at NCI's expense.

11. REPORTING ADVERSE EVENTS AND DEVIATIONS

DEFINITION: AE means any untoward medical occurrence associated with the use of a drug in humans, whether or not considered drug related. An AE can therefore be any unfavorable and unintended sign), symptom, or disease temporally associated with participation in a study, whether or not related to that participation. This includes all deaths that occur while a participant is on a study.

Please note that all abnormal clinical laboratory values that are determined to be of clinical significance based on a physician's assessment are to be reported as AEs. Those labs determined to be of no clinical significance or of unknown clinical significance (per the physician's assessment) should not be reported as AEs. Any lab value of unknown clinical significance should continue to be investigated/followed-up further for a final determination, if possible.

A list of AEs that have occurred or might occur (Reported Adverse Events and Potential Risks) can be found in Section 6.2, Pharmaceutical Information, as well as the Investigator Brochure or package insert.

11.1 Adverse Events and Deviations

11.1.1 Reportable Adverse Events (AEs)

All AEs that occur after the informed consent is signed and baseline assessments are completed must be recorded on the AE CRF (paper and/or electronic) whether or not related to study agent.

11.1.2 AE Data Elements:

The following data elements are required for adverse event reporting.

- AE verbatim term
- System Organ Class (SOC)

- Common Terminology Criteria for Adverse Events v4.0 (CTCAE) AE term
- Event onset date and event ended date
- Severity grade
- Attribution to study agent (relatedness)
- Whether or not the event was reported as a serious adverse event (SAE)
- Whether or not the subject dropped due to the event
- Outcome of the event

11.1.3 Severity of AEs

11.1.3.1 Identify the AE using the NCI Common Terminology Criteria for Adverse Events (CTCAE) version 4.0. The CTCAE provides descriptive terminology and a grading scale for each adverse event listed. A copy of the CTCAE can be found at

http://ctep.cancer.gov/protocolDevelopment/electronic_applications/ctc.htm

All AEs, including injection site reactions, will be assessed according to the CTCAE grade associated with the AE term. AEs that do not have a corresponding CTCAE term will be assessed according to the general guidelines for grading used in the CTCAE v4.0. as stated below. AEs will be reported and evaluated by use of the standard Adverse Events case report form (CRF).

CTCAE v4.0 general severity guidelines:

Grade	Severity	Description
1	Mild	Mild; asymptomatic or mild symptoms; clinical or diagnostic observations only; intervention not indicated.
2	Moderate	Moderate; minimal, local or noninvasive intervention indicated; limiting age-appropriate instrumental activities of daily living (ADL)*.
3	Severe	Severe or medically significant but not immediately life-threatening; hospitalization or prolongation of hospitalization indicated; disabling; limiting self-care ADL**.
4	Life-threatening	Life-threatening consequences; urgent intervention indicated.
5	Fatal	Death related to AE.

ADL

*Instrumental ADL refers to preparing meals, shopping for groceries or clothes, using the telephone, managing money, etc.

**Self-care ADL refers to bathing, dressing and undressing, feeding self, using the toilet, taking medications, and not bedridden.

11.1.3.2 Injection Site Reactions

Injection site reactions, a subset of all AEs, will also be reported by use of a participant-completed Vaccine Report Card, captured on a separate CRF, and reported to NCI, DCP. This report will not be part of the MDS. The following guidelines will be used to evaluate the injection site reaction:

Local Reaction to Injectable Product	Mild (Grade 1)	Moderate (Grade 2)	Severe (Grade 3)	Potentially Life Threatening (Grade 4)
Pain	Does not interfere with activity	Repeated use of non-narcotic pain reliever > 24 hours or interferes with activity	Any use of narcotic pain reliever or prevents daily activity	Emergency room (ER) visit or hospitalization
Tenderness	Mild discomfort to touch	Discomfort with movement	Significant discomfort at rest	ER visit or hospitalization
Erythema/Redness*	2.5 - 5 cm	5.1 - 10 cm	> 10 cm	Necrosis or exfoliative dermatitis
Induration/Swelling**	2.5 - 5 cm and does not interfere with activity	5.1 - 10 cm or interferes with activity	> 10 cm or prevents daily activity	Necrosis

* In addition to grading the measured local reaction at the greatest single diameter, the measurement should be recorded as a continuous variable.

** Induration/Swelling should be evaluated and graded using the functional scale as well as the actual measurement.

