Pain at the injection site without touching		 None  A little, but it didn’t interfere with normal activity  Some, required OTC* medications for more than 24 hours or limited normal activity  A lot, required prescription medications, interfered with normal activity  Required ER visit or hospitalization	 None  A little, but it didn’t interfere with normal activity  Some, required OTC* medications for more than 24 hours or limited normal activity  A lot, required prescription medications, interfered with normal activity  Required ER visit or hospitalization	 None  A little, but it didn’t interfere with normal activity  Some, required OTC* medications for more than 24 hours or limited normal activity  A lot, required prescription medications, interfered with normal activity  Required ER visit or hospitalization	

Possible side effects	Date Symptom Appeared	2 days after injection Date _____	7 days after injection Date _____	14 days after injection Date _____	Date Symptom Disappeared

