Tenderness (Pain at the injection site with touch)		 None  A little, but it didn't interfere with normal activity  Some, required OTC* medications for more than 24 hours or limited normal activity  A lot, required prescription medications, interfered with normal activity  Required ER visit or hospitalization	 None  A little, but it didn't interfere with normal activity  Some, required OTC* medications for more than 24 hours or limited normal activity  A lot, required prescription medications, interfered with normal activity  Required ER visit or hospitalization	 None  A little, but it didn't interfere with normal activity  Some, required OTC* medications for more than 24 hours or limited normal activity  A lot, required prescription medications, interfered with normal activity  Required ER visit or hospitalization	
Swelling/ Induration**		 None  Yes. It measured _____ centimeters	 None  Yes. It measured _____ centimeters	 None  Yes. It measured _____ centimeters	
Itching at site		 None  Yes	 None  Yes	 None  Yes	
Skin warmth at site		 None  Yes	 None  Yes	 None  Yes	

* OTC – Over the counter medications such as Tylenol® or ibuprofen.

** Firm, raised swelling.

If you experience any other symptoms that you would like to report, please make note of them on this page. Be sure to write down the date the symptom appeared and the date the symptom disappeared. If you took any medications for the symptom or visited a doctor or hospital for the symptom, please inform the study team.

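### The Vaccine Report Card does not collect the items that the section 11.1.3.2 table uses to grade induration, tenderness grades 2–3 and the pain grade 2/3 boundary

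*Combined protocol and SAP*

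**What the plan says.** Section 11.1.3.2 states that injection site reactions will also be reported on a participant-completed Vaccine Report Card and captured on a separate CRF. It introduces its grading table with "The following guidelines will be used to evaluate the injection site reaction". The relevant cells are:

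- Induration: grades 1–3 combine diameter with effect on activity, and the note reads "Induration/Swelling should be evaluated and graded using the functional scale as well as the actual measurement".
- Tenderness: grade 1 is mild discomfort on touch, grade 2 is "Discomfort with movement", grade 3 is "Significant discomfort at rest", and grade 4 is an ER visit or hospital stay.
- Pain: grade 2 is "Repeated use of non-narcotic pain reliever > 24 hours or interferes with activity" and grade 3 is "Any use of narcotic pain reliever or prevents daily activity".

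The card in Appendix E, completed at days 2, 7 and 14, asks for swelling as none or a number of centimetres. Pain and tenderness share one set of options. The two middle ones are "Some, required OTC* medications for more than 24 hours or limited normal activity" and "A lot, required prescription medications, interfered with normal activity". The card's instructions define tenderness as pain on touch. They send aching felt without touch, including when moving or seated, to the separate pain item.

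Participant-reported injection site reactions are a secondary objective (1.2) and endpoint (8.2, 13.1). They are to be summarised descriptively and compared between arms (13.5, item 5). Section 13.7 calls the report card analysis exploratory.

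**The concern.** A grading table can be applied only if the form supplies its inputs. Here the protocol names the form and the table together, yet several grade criteria have no field on the form. If the table is applied to the card as printed, an analyst must grade induration on size alone, invent a rule for tenderness, and decide what the strongest non-emergency pain option means. Different choices give different severity tables for the same cards. Grading induration on size alone also errs in one direction, because a small swelling that limits activity is graded too low. What is at stake is the credibility of the by-arm description of local reactions, in a trial whose report card letter says it wants the vaccine experience documented carefully.

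**Working it through.** No power, alpha or sample size figure is involved, so the check is a comparison of criteria. The inputs are the 11.1.3.2 table and its notes, the Appendix E instructions and card, and three other places that might supply a missing item: 5.4 (concomitant medications), 7.3 (staff check) and 11.1.3.1 (CTCAE grading).

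**Induration.** The table needs diameter and effect on activity. The card gives diameter only. In the table, interference with activity is enough for grade 2 and prevented activity is enough for grade 3, so each size band maps as follows, leaving necrosis (grade 4) aside:

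- 2.5–5 cm: grade 1 if there is no interference, 2 if there is interference, 3 if activity is prevented.
- 5.1–10 cm: grade 2, or 3 if activity is prevented.
- Over 10 cm: grade 3 on size alone.

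Diameter therefore fixes a floor. Even grade 1 cannot be confirmed, because it requires the absence of interference. Necrosis is not asked either.

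**Tenderness.** Grade 4 matches the card's last option. Grade 1 matches the mildest option loosely. Grades 2 and 3 turn on movement and rest, and no tenderness option mentions either. Discomfort of that kind is recorded, if at all, under pain, where movement and rest are not distinguished.

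**Pain.** Grades 1, 2 and 4 match closely. Grade 3 does not:

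- A non-narcotic prescription drug with interference is grade 2 in the table but fits the card's "A lot, required prescription medications, interfered with normal activity".
- Pain that prevents daily activity without a prescription drug is grade 3 in the table and has no card option.
- The table joins its two grade 3 conditions with an or. The card runs its two together.

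The possible errors at this boundary therefore go in both directions.

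**Erythema.** Diameter supports grades 1–3. Only grade 4 (necrosis or exfoliative dermatitis) is not collected.

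**Other sources.** Section 5.4 records each medication with its indication, and Appendix E asks participants to write down what they took for symptoms, so narcotic use may be recoverable. The staff check in 7.3 covers diameter only, at Weeks 2 and 12, and only if a reaction persists. The grading in 11.1.3.1 uses CTCAE, a different scale. No described source asks whether a swelling or pain interfered with or prevented activity in the table's terms, or separates movement from rest for tenderness.

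**The case against.** The strongest reply is that the separate CRF named in 11.1.3.2 is not among the documents and might hold staff-assessed items. Section 7.1 schedules an adverse event and medication review about two weeks after every injection (Weeks 2, 4, 12 and 55), so staff could ask about activity. This stands as a limit on certainty. It does not remove the disagreement, because no functional, movement or rest question is described anywhere, and the card is the only instrument shown.

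The second reply is that formal safety grading does not use the card. Section 11.1.3.1 grades all adverse events, injection site reactions included, by CTCAE on the standard form, and the stopping rule in 13.7.1 works on adverse event grades. This stands in full and sets the scope of the point.

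The third is that 1.2 and 8.2 name reaction events, not grades, so the card's categories and centimetres could simply be tabulated as collected. This is fair for 13.5, but it leaves the grading instruction in 11.1.3.2 unmet.

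A reader might infer that these reactions cannot be graded at all, that the arm comparison will be misgraded, or that every card is affected (4 injections × about 110 participants = about 440). The documents support none of these. Partial grading is possible for each reaction, no graded comparison or test is specified, and only reactions where the criteria diverge can be misgraded. Half the participants receive saline, and the pilot reported nothing above grade 1 in over 150 vaccinations (2.3), although its grading scale is not stated.

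**Conclusion.** The card and the table contradict each other and must be reconciled. Three of the four graded reactions are affected, to different degrees. Induration is the clearest, because an explicit instruction cannot be met from the card and size alone can only under-grade. Tenderness is affected at grades 2 and 3. Pain is affected only at the grade 2/3 boundary and is partly repairable from medication records. The consequence is limited to the descriptive participant-reported endpoint. The primary analysis, the decisions to proceed between Parts, CTCAE reporting and the stopping rule are untouched. How many reactions fall in the ambiguous region is unknown. The conclusion assumes that the unseen CRF adds no functional or movement/rest items. If it does, the protocol should say so.

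**What to change.** Make the two agree before analysis, by whichever route the sponsor prefers:

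1. Add to the card, or to the CRF that captures it, an activity question for swelling, movement and rest options for tenderness, and separate responses for interfering with versus preventing activity and for narcotic versus other prescription drugs. Change the tenderness instructions to match.
2. Or revise the induration, tenderness and pain rows of 11.1.3.2 to what the card collects, and withdraw the functional-grading note.

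Under either route, pre-specify how cards already completed map to grades. Report induration as a minimum grade where function was not recorded, and use the concomitant medication CRF to identify narcotic use.

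The cost is a form revision with IRB approval, plus the sponsor's review of any amended CRF (12.2). The mapping rule for existing cards cannot recover answers that were never asked for, so earlier and later cards may need separate presentation. Route 2 avoids changing the card but gives up the functional grading that the protocol now asks for.
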